6.3 PRIMARY ANALYSES

The primary objective of this study is to investigate whether baseline CSF mHTT is a predictor of the change from baseline to 15 months for the following variables:

- Clinical endpoints (cUHDRS, TFC, TMS, SDMT, SWR, and IS)
- CSF and blood biomarkers
- Brain imaging (MRI)

Initially, a linear model will be used to evaluate the association between each response variable (e.g., change from baseline to 15 months in cUHDRS) and baseline CSF mHTT without adjustment for any baseline characteristics.

The same model will then be considered again, adjusting for baseline level of the response variable (e.g., baseline cUHDRS), baseline CSF mHTT levels, CAG, and baseline CAP (the latter defined as the product of age at baseline by [CAG—33.66] (Zhang et al. 2011). A sensitivity analysis to evaluate the impact of additional baseline characteristics (e.g., gender, education level) may be performed.

Other approaches may be used in the case of severe multicollinearity, which would result in model instability.

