6.4 SECONDARY ANALYSES

The secondary objective for this study is to investigate the within-patient change from baseline in CSF mHTT levels and the association between changes from baseline in CSF mHTT levels at 3, 9, and 15 months and changes in clinical measures (cUHDRS, TFC, TMS, SDMT, SWR, and IS), biomarkers of neuronal injury, and brain atrophy endpoints.

Initially, a linear model will be used to evaluate the association between each response variable (e.g., change from baseline to 15 months in CSF NfL levels) and the change in CSF mHTT level, without adjustment for any baseline characteristics. A similar model will then be considered, adjusting for baseline level of the response variable, CAG, and baseline CAP. A sensitivity analysis to evaluate the impact of additional baseline characteristics (e.g., baseline mHTT, gender, education level) may be performed.

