### **Changes from Version 2 to Version 3**

The changes were mainly done to address identified inconsistencies or to increase clarity of the paragraphs.

Section 4.4 clarified further definition of baseline for clinical assessments with multiple predose measurements and for companion assessments.

Sections 4.5.1.6 and 4.5.1.7 corrected the value of the higher score and, as in section 4.5.1.12, corrected the definition of the direction of worsening /improvement for the change from baseline.

In Table 3 “country” was added as covariate where was previously omitted in error.

Section 4.7.3 and 4.7.3 corrected sentence on the use of local ranges for labs values.

Section 4.7.7 changed to aligned CSSR “Improvement on Suicidal ideation” derivation with the other studies in the program.

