## 1. BACKGROUND

This Statistical Analysis Plan (SAP) describes all planned methods of summarizing and analyzing data to be collected in Study BN40422.

Study BN4022 is a multi-site, prospective, 15-month longitudinal, cohort study measuring cerebrospinal fluid (CSF) mutant huntingtin protein (mHTT) in patients with early manifest Stage I or Stage II Huntington's disease (HD).

This longitudinal study in patients with early HD will explore the prognostic value of baseline CSF mHTT; the relationship of CSF mHTT to other key biological markers in the putative causal pathway; rate and variability of CSF mHTT increase in untreated patients; and the utility of recording clinical outcome measures via sensors contained in the Roche HD mobile app. Since no study medication will be given to the patients, safety assessments will consist of monitoring and recording adverse events (AEs), including serious adverse events (SAEs), related to study procedures.

[figure not shown]
The SAP language supersedes the language in the Protocol and Protocol Synopsis (where specified).

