### **2.2.1 Primary Endpoints**

The primary objective of this study is to examine the predictive value of baseline cerebrospinal fluid (CSF) mHTT levels on measures of disease progression using the following endpoints:

- Change from baseline in the following clinical endpoints at 3, 9, and 15 months: composite Unified Huntington's Disease Rating Scale (cUHDRS), Total Functional Capacity Scale (TFC), Total Motor Scale (TMS), Symbol Digit Modalities Test (SDMT), Stroop Word Reading (SWR) Test, and Independence Scale (IS)
- Change from baseline in biomarkers of neuronal injury (e.g., CSF neurofilament light chain [NfL] and tau) at 3, 9, and 15 months
- Change from baseline in brain atrophy endpoints (e.g., whole brain volume decline, caudate volume decline) as determined by brain MRI, at 3, 9, and 15 months

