### **2.2.2 Secondary Endpoints**

The secondary objective of this study is to investigate the temporal profile of longitudinal CSF mHTT changes within patient, and the association of these changes with corresponding changes in biomarkers of neuronal injury (e.g., CSF NfL and tau) and clinical outcomes using the following endpoints:

- Within-patient change from baseline in CSF mHTT levels at 3, 9, and 15 months
- Association of change from baseline in CSF mHTT levels at 3, 9, and 15 months and:
  - Change from baseline in clinical measures (cUHDRS, TFC, TMS, SDMT, SWR, and IS) at 3, 9, and 15 months.
  - Change from baseline in biomarkers of neuronal injury (e.g., CSF NfL and tau) at 3, 9, and 15 months.
  - Change from baseline in brain atrophy endpoints, as determined by brain MRI at 3, 9, and 15 months.

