##### **4.5.2.2 Model-based Analyses**

In order to model the relationship between a continuous response variable (e.g. the change in cUHDRS) and a main predictor (e.g. change in CSF mHTT) at a given time-point, a linear regression model (LRM) will be used. At each time point only those data from visit occurring  $\pm$  56 days from the scheduled visit will be used.

The full list of analyses which will be considered, together with specifications about additional covariates to account for, is provided in [Table 3](#). Additional analyses, not listed in this SAP, may be conducted to better understand any safety concern which may arise.

Least squares means (LSM) estimates, at each time-point, for the slope of the main predictor (X-variable in [Table 3](#)) along with corresponding standard error, 95% CI and unadjusted p-value will be presented. The estimated effect represents the effect of the main predictor on the response adjusted for all other covariates in the model. Distributional assumptions underlying the model used for analysis will be examined to gain confidence that the model assumptions are reasonable and where needed, sensitivity analyses will be performed.

The procedure that will be used to fit linear regression in SAS is as follows:

```
proc mixed data=dataname plots=all;
class
model y-variable= x-variable + {additional covariates in Table 3} /ddfmi=kr cl;
ods output solutionf=outputname;
run;
```

In addition to [Table 3](#), scatter plots and Spearman correlations will be calculated among all baseline fluid biomarkers at baseline. Similar analyses will be performed for CAG and CAP with baseline fluid biomarkers, baseline CSF mHTT and baseline cUHDRS (including individual components). CAP is defined by the product of (CAG – 33.66) by baseline age.

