**Table 3 Overview of Planned Outputs to Describe the Association Between Selected Pairs of Parameters at Final analysis.**

Paired Variables	Data Type				Time points	Additional covariates in statistical models		
	X-variable		Y-variable					
	Absolute	Change	Absolute	Change				
X=mHTT, Y=Clinical Endpoints §	Y		Y		X & Y=BSL	BSL-Age, CAG, CAP, Country		
	Y			Y	X=BSL, Y=15M	BSL- Clin.endp, BSL-Age, CAG, CAP, Country		
		Y		Y	X=3M, 9M, 15M, Y=15M	BSL- Clin.endp, BSL-mHTT, BSL-Age, CAG, CAP, Country		
X= CSF Biomarkers, Y=Clinical Endpoints	Y		Y		X & Y=BSL	BSL-Age, CAG, CAP, Country		
	Y			Y	X=BSL, Y=15M	BSL- Clin.endp, BSL-Age, CAG, CAP, Country		
		Y		Y	X=3M, 9M, 15M, Y=15M	BSL- Clin.endp, BSL-CSF.Biom, BSL-Age, CAG, CAP, Country		
X=mHTT, Y=CSF Biomarkers *	Y		Y		X & Y=BSL	BSL-Age, CAG, CAP		
	Y			Y	X=BSL, Y=15M	BSL- CSF.Biom, BSL-Age, CAG, CAP		
		Y		Y	X & Y=3M, 9M, 15M	BSL-CSF.Biom, BSL-mHTT, BSL-Age, CAG, CAP		
X=CSF-NfL, Y=Plasma-NfL	Y		Y		X & Y=BSL	None		
		Y		Y	X & Y=3M, 9M, 15M	None		
X=mHTT, Y=normalised MRI	Y		Y		X & Y=BSL	BSL-Age, CAG, CAP		
X=CSF-Biom Y=normalised MRI	Y		Y		X & Y=BSL	BSL-Age, CAG, CAP		
X=mHTT, Y=BSI *	Y			Y (%-change)	X=BSL, Y=3M, 9M, 15M	BSL-Age, CAG, CAP		
		Y		Y (%-change)	X=3M, 9M, 15M, Y=15M	BSL-mHTT, BSL-Age, CAG, CAP		
X=CSF-Biom, Y=BSI *		Y		Y (%-change)	X=3M, 9M, 15M, Y=15M	BSL-Biom, BSL-Age, CAG, CAP		

**Table 3 Overview of Planned Outputs to Describe the Association Between Selected Pairs of Parameters at Final analysis (cont.)**

BSL= baseline; BSI= boundary shift integral; mHTT=mutant huntingtin protein; CAP= =(CAG-33.66)\* AGE\_BASELINE; CSF= cerebrospinal fluid; NfL= neurofilament light chain; MRI= magnetic resonance imaging.

§ Clinical Endpoints will include cUHDRS, TFC, TMS, SDMT and SWR

+ CSF Biomarkers will include NFL, YKL-40 and Tau

‡ MRI Volume

\* BSI is already a measure of change thus the change is not derived.

In case of an interim analysis (see Section 4.9) the analyses will be based on the available data (e.g. up to 9 months) by the clinical cutoff date.

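### SAP Table 3 plans no mHTT association model for the Independence Scale, a named primary and secondary endpoint, and the SAP contradicts itself on an MMRM for that scale

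*SAP*

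**What the plan says.** Both objectives concern association with CSF mHTT, and both name IS.

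- **Primary.** The clinical list in SAP 2.2.1 ends with "Symbol Digit Modalities Test (SDMT), Stroop Word Reading (SWR) Test, and Independence Scale (IS". Protocol 6.3 gives the responses to be regressed on baseline mHTT as "Clinical endpoints (cUHDRS, TFC, TMS, SDMT, SWR, and IS".
- **Secondary.** SAP 2.2.2 pairs change in mHTT with "Change from baseline in clinical measures (cUHDRS, TFC, TMS, SDMT, SWR, and IS) at 3, 9, and 15 months". Protocol 6.4 likewise refers to "changes in clinical measures (cUHDRS, TFC, TMS, SDMT, SWR, and IS), biomarkers of neuronal injury, and brain atrophy endpoints".
- **Models.** SAP 4.5.2.2 states: "The full list of analyses which will be considered, together with specifications about additional covariates to account for, is provided in" Table 3. The Table 3 footnote then defines the clinical endpoints: "Clinical Endpoints will include cUHDRS, TFC, TMS, SDMT and SWR".
- **Precedence.** SAP section 1 says: "The SAP language supersedes the language in the Protocol and Protocol Synopsis (where specified".
- **Change over time.** SAP 4.5.1.4 treats IS as continuous and promises MMRM results for it, citing Section 4.5.1 and Table 2. In Table 2, the UHDRS row (whose footnote includes IS) marks the MMRM as performed for every parameter but IS.

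**The concern.** A scale listed as a primary and secondary endpoint has no model in the SAP that addresses either objective. Two analysts, one working from the SAP and one from Protocol 6.3, would report five and six primary clinical slopes respectively. An IS model added later under SAP 4.5.3 would not be pre-specified in the SAP, so a reader could not tell whether it was run, or left out, after the data were seen. The MMRM conflict is a separate drafting fault: it affects only the description of IS over time, because that model contains no mHTT term.

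**Working it through.** The documents give no figure to reproduce here. The check compares lists and then counts models.

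**1. Endpoint lists**

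| Source | cUHDRS | TFC | TMS | SDMT | SWR | IS |
|---|---|---|---|---|---|---|
| SAP 2.2.1, 2.2.2 | yes | yes | yes | yes | yes | yes |
| Protocol 6.3, 6.4 | yes | yes | yes | yes | yes | yes |
| Synopsis in SAP Appendix 1 | yes | yes | yes | yes | yes | yes |
| SAP Table 3 footnote | yes | yes | yes | yes | yes | **no** |

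The lists differ by IS alone.

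**2. Other SAP routes to an mHTT-IS result**

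- Scatter plots (4.5.2.1) are drawn for the pairs in Table 3, so they inherit the gap.
- The added Spearman correlations (4.5.2.2) relate baseline fluid biomarkers to each other, and CAG and CAP to those biomarkers, baseline mHTT and baseline cUHDRS with its components. The cUHDRS formula (4.5.1.3.5) uses TFC, TMS, SDMT and SWR, so IS is not a component.
- The MMRM (4.5.1) adjusts for the baseline value, CAG, age, CAP, country and time, with no mHTT term.
- The allowance for unlisted analyses in 4.5.2.2 is confined to safety concerns. Section 4.5.3 permits further exploratory work but specifies none.
- Interim analyses (4.9) follow the same plan.

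**3. Precedence rule**

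The rule ranks the SAP over the protocol. It cannot settle a conflict between SAP 2.2.1 and 2.2.2 on one side and SAP Table 3 on the other. If its qualifier leaves Protocol 6.3 in force for IS, the adjustment would differ from that for the other five endpoints: Protocol 6.3 adjusts for the baseline response, CAG and CAP, while Table 3 also includes baseline age and country.

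**4. Count of models, at Table 3's own time points**

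For each clinical endpoint, the mHTT rows give:

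- 1 baseline cross-sectional model, which serves neither objective;
- 1 model of baseline mHTT against 15-month change (primary);
- 3 models of mHTT change at 3, 9 and 15 months against 15-month change (secondary).

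Needed for six endpoints: 6 × (1 + 3) = 24, that is 6 primary and 18 secondary.

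Supplied for five endpoints: 5 × (1 + 3) = 20, that is 5 primary and 15 secondary.

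Missing: 24 − 20 = 4, all for IS (1 primary, 3 secondary). The cross-sectional row would add one more.

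**5. Nominal resolution of the scale**

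IS runs from 10 to 100 in steps of 5: (100 − 10)/5 + 1 = 19 levels. TFC runs from 0 to 13: 14 possible scores. TFC is modelled, so the nominal number of levels does not explain the exclusion of IS.

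**6. MMRM for IS**

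Section 4.5.1.4 says yes and Table 2 says no. Neither gives a reason.

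**The case against.** The strongest reply is that the exclusion was deliberate. Table 2 explicitly exempts IS from the MMRM. Read with Table 3, it suggests a consistent choice to describe IS but not model it, with the endpoint lists and 4.5.1.4 left unrevised. On that reading 4.5.1.4 carries a stock sentence that defers to Table 2. This is possible, but the SAP does not say so, and the endpoint lists still promise the association. The remedy below leaves that choice open. An analyst may reasonably favour Table 2 on the MMRM, but the two instructions are still opposite.

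Other points have partial force:

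- **The amendment record.** Each of the three SAP amendments records a change to Table 3, and one says that country "was added as covariate where was previously omitted in error". None mentions IS. If IS was absent from the start, that silence is expected. It shows that no reason is recorded, not that the omission was an error.
- **Ceiling effects.** The comparison of 19 with 14 levels is nominal. Protocol 4.2 expects mostly Stage I patients, and the documents give no IS distribution, so a ceiling can be neither shown nor ruled out.
- **Redundancy.** Protocol 3.3.2.1 describes IS as highly correlated with TFC, which limits the practical loss. But Table 3 models cUHDRS together with all four of its components, so overlap is not the rule by which it excludes scales.
- **The denominator.** SAP 2.2.1 names 3, 9 and 15 months. Taken literally, that means 6 × 3 = 18 primary pairings, of which Table 3 supplies 5. The count of 24 holds only for Table 3's time points. The statement that one endpoint in six is missing does not depend on that choice.
- **Consequence.** The study is exploratory, and IS will still be tabulated and plotted. This caps the importance of the point but does not remove it.

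**Conclusion.** The concern holds. As written, the SAP specifies no mHTT model for one of its six named primary and secondary clinical endpoints, and no other provision supplies one. On Table 3's time points, 4 of 24 objective-related models are missing: 1 of 6 primary and 3 of 18 secondary. The conclusion rests on taking Table 3 as exhaustive, which is how 4.5.2.2 describes it. The contradictory MMRM instructions for IS are a second, smaller fault. There is no formal hypothesis test, so neither type I error nor power is at issue. Both faults should be corrected before the final analysis, because they decide what is reported against stated objectives.

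**What to change.** 1. Add IS to the clinical-endpoint definition for the mHTT rows of Table 3, with the covariates already listed there. Alternatively, remove IS from the primary and secondary endpoint lists and state why.
2. Make SAP 4.5.1.4 and Table 2 agree on whether an MMRM is fitted to IS, with a reason if it is not.
3. Two lesser alignments with Protocol 6.3 can be made in the same edit. That section includes blood biomarkers, but Table 3 has no row for mHTT against plasma NfL; add one for baseline mHTT against 15-month change. It also plans an unadjusted mHTT model first, whereas every mHTT row in Table 3 carries covariates; report the unadjusted slope as well, or state that it is dropped.

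For IS the cost is wording plus four regressions, or five with the cross-sectional row. Protocol Appendix 2 already schedules IS at all clinic visits, so no new data are needed. The addition should be limited to the mHTT rows: the same label is used for the CSF-biomarker rows, where including IS would add 3 biomarkers × 5 models = 15 more.

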#### **4.5.3 Exploratory Analysis**

Additional exploratory analyses may be performed as appropriate. Data from this study may be combined with data from other studies to inform disease and causal models.

### **4.6 PHARMACOKINETIC AND PHARMACODYNAMIC ANALYSES**

No study medication will be given to the patients therefore no pharmacokinetic or pharmacodynamic analysis will be conducted.

### **4.7 SAFETY ANALYSES**

Safety information will be collected, reviewed, and evaluated by the Sponsor or designee in accordance with the Safety Management Plan throughout the conduct of the clinical trial. Data will be summarized using descriptive statistics. Only scheduled visits will be presented in summary tables and both scheduled and unscheduled visits will be included in listings. All enrolled patients will be used for listings; safety population will be used for summary statistics.

Adverse event reports will not be derived from patient-reported outcome (PRO) or observer-reported outcome (ObsRO) data by the Sponsor, and safety analyses will not be performed using PRO or ObsRO data. Sites are not expected to review the PRO or ObsRO data for adverse events.

Additional analysis to the one outlined below may be conducted depending on emerging safety data. ).

Where applicable, in order to account for delays in the visit due to covid-19 a time window of +- 56 days from the expected scheduled visit will be applied to summary tables and plots (details in the list of planned output (LOPO)).

#### **4.7.1        Exposure of Study Medication**

No study drug will be given during this study.

#### **4.7.2        Adverse Events**

Since no study medication will be given to the patients, safety assessments will consist of monitoring and recording adverse events, including serious adverse events, related to study procedures.

Adverse events and SAEs related to a study procedure reported from date of informed consent until the patient's last visit or withdrawal, will be analyzed.

All AE will be listed, any AE which starts after the reference time point (see Section 4) will be summarized.

The number of unique patients who experience and report an adverse event, each adverse event, and the number of adverse events themselves will be tabulated by medical dictionary for regulatory activities (MedDRA) System Organ Class and Preferred Term. Adverse events will also be summarized by severity.

Serious AEs, AEs that lead to study discontinuation and deaths will also be analysed separately. Selected adverse events may be summarized and listed separately.

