4.5.6 Collection of Cerebrospinal Fluid (Lumbar Puncture Procedure)

Patients will have CSF collected at baseline and at Months 3, 9, and 15. Prior to performing each scheduled lumbar puncture, local laboratory analysis of coagulation factors (INR and/or PT, aPTT) and platelets must be conducted and results reviewed. Collection for these local labs may occur at any time in the 72 hours prior to the lumbar puncture. The lumbar puncture should be performed at approximately the same time at each visit (ideally in the morning between 08:00 and 12:00 hours) to minimize potential diurnal variation of CSF parameters. CSF fluid (20 mL) is to be collected for analyses using a standard lumbar puncture collection kit. If there are difficulties in collecting 20 mL of CSF fluid, a minimum of 15 mL should be collected. A 24G Whitacre (atraumatic) needle should be used. Depending on institutional guidelines, local anesthesia may be used for the procedure. Sedation *is not allowed*. Spinal ultrasound may be used for the lumbar puncture procedure if deemed necessary, but is not required. Ultrasound guidance may be used if attempts at lumbar puncture without imaging are unsuccessful, if it is local practice to use ultrasound, or if institutional guidelines dictate use of ultrasound with each lumbar puncture. *Fluoroscopy guidance can also be used, if local institutional guidelines dictate and if locally required approvals of the technique are obtained, but it is not required. Where fluoroscopy is used, patients should also be informed and consent obtained.*

If there is the occurrence of a failed CSF collection procedure due to inadequate establishment of access to the IT space, a second attempt may occur up to 14 days after the original attempt. For this additional visit, local laboratory analysis of coagulation factors (INR and/or PT, aPTT) and platelets must be conducted and the results reviewed, within 72 hours prior to performing the LP. In addition, neurological examination, vital signs and a review of AEs and concomitant medication should occur as part of the safety and tolerability evaluations on the day of LP.

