5.3.5.6 Deaths

All deaths that occur during the protocol-specified adverse event reporting period (see Section 5.3.1), regardless of relationship to study procedure, must be recorded on the Adverse Event eCRF and immediately reported to the Sponsor (see Section 5.4.2).

Death should be considered an outcome and not a distinct event. The event or condition that caused or contributed to the fatal outcome should be recorded as the single medical concept on the Adverse Event eCRF. Generally, only one such event should be reported. If the cause of death is unknown and cannot be ascertained at the time of reporting, "**unexplained death**" should be recorded on the Adverse Event eCRF. If the cause of death later becomes available (e.g., after autopsy), "unexplained death" should be replaced by the established cause of death. The term "**sudden death**" should not be used unless combined with the presumed cause of death (e.g., "sudden cardiac death").

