6.5 SAFETY ANALYSES

The safety analysis population will consist of all patients who underwent study-specific procedures. Given the non-drug nature of this study, limited safety analyses will be reported.

The number of unique patients who experience and report an adverse event, each adverse event, and the number of adverse events themselves will be tabulated by MedDRA System Organ Class and Preferred Term. Adverse events will also be summarized by severity (see Section [5.3.3](#)).

Laboratory absolute values at screening will be listed and summarized descriptively. Values outside the normal range will be listed and summarized.

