### **4. STATISTICAL METHODS**

This is longitudinal prospective cohort study and it is exploratory in nature. As such, there is no predefined hypothesis testing, and all analyses will be regarded as exploratory. Where applicable, parameter estimates will be reported together with 95% CI. p-values may still be reported. Basic assumptions of the proposed analyses will be checked, and data transformation (e.g., logarithm transformation) or other analyses could be carried out, if appropriate.

Any patient data listings will be presented for all patients enrolled into the study.

Descriptive summary statistics including but not limited to n, mean, median, SD, range (minimum, maximum) for continuous variables, and counts and percentages for categorical variables will be used to summarize most data by visit.

Study day will be calculated from a reference date, there is no Day 0, as follows:

- Study Day=assessment date – reference date+1,  
if the assessment date is on or after the reference date; or
- Study Day=assessment date – reference date,  
if the assessment date is earlier than the reference date

The reference date for patients who had at least one lumbar puncture (attempted or successful) is the date of the last lumbar puncture for visit Day 1. For patients who did not have a lumbar punctures (LP) the reference date is the date of enrollment in the study (via the interactive voice or web-based response system [IxVRS] system).

For all analysis, where applicable, the value for age, gender and disease stage as reported in the clinical database as well as the value of CAG repeats as measured by the central lab will be used instead of the values coming from IxVRS system.

For all analysis the clinical cutoff date will be applied for all data, i.e. data occurring after the clinical cutoff date will not be included in the analysis.

The fact that patients in this study are matched to the BN40697 study may offer the future opportunity to compare the current observational study against the OLE study. Details of this analysis are not in the scope of this SAP (neither will be reported in the Clinical Study Report [CSR] of Study BN40422) and may be described in a separate document.

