#### **4.4 BASELINE DEFINITIONS**

For vital signs (blood pressure [BP], heart rate [HR], respiration rate by position and temperature), baseline will be defined as the average of the available values collected prior to first LP (attempt or successful lumbar puncture) (Screening, Study Day –1 and Study Day 1).

For CSF baseline will be defined as the last available CSF sample collected (Study Day –1 or Study Day 1).

For clinical endpoints ( patient-, observer-, clinician-reported and performance outcomes) measured multiple times before first lumbar puncture (successful or attempt), baseline will be defined as the first available measure prior to the first lumbar puncture (successful or attempt) (Screening, Study Day –1 and Study Day 1). Otherwise the only measurement before the first LP will be used. For the observer reported outcomes any measurement occurring on the same day of the first LP, irrespective if it was before or after the LP, can be used for the evaluation of the baseline.

For the Columbia Suicide Severity Scale questionnaire see Section [4.7.7](#) .

For all other measures and parameters, baseline will be defined as the last non-missing measure prior to last lumbar puncture (successful or attempted) (Screening, Study Day –1 and Study Day 1), unless specified otherwise.

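### Read with the Section 4 reference date, SAP 4.7.2 would list but not tabulate adverse events that start between a failed baseline lumbar puncture and its repeat on a later day

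*SAP*

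**What the plan says.** **The summary rule.** SAP 4.7.2 puts every AE in the listing. For the summaries it says that "any AE which starts after the reference time point (see Section 4) will be summarized". The sentence just before it says that AEs and serious AEs "related to a study procedure reported from date of informed consent" up to the last visit or withdrawal will be analysed.

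**The reference.** Under SAP Section 4, for a patient with at least one LP, attempted or successful, the reference date "is the date of the last lumbar puncture for visit Day 1".

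**The repeat puncture.** Under protocol 4.5.6, when CSF collection fails for lack of access to the intrathecal space, "a second attempt may occur up to 14 days after the original attempt". Baseline is not excepted. At that additional visit, "a review of AEs and concomitant medication should occur as part of the safety and tolerability evaluations on the day of LP".

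**Other anchors.** SAP 4.4 takes the vital-signs baseline from values before the first LP, and SAP 4.7.7 counts the C-SSRS endpoints from the first LP. For measures with no rule of their own, SAP 4.4 says that "baseline will be defined as the last non-missing measure prior to last lumbar puncture (successful or attempted". Protocol 6.5 says that AEs "will be tabulated by MedDRA System Organ Class and Preferred Term" and sets no onset limit.

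**The concern.** Protocol 5.2.1 defines an AE in this study by its relation to a protocol-mandated intervention and gives lumbar puncture as the example. Apart from deaths, which "regardless of relationship to study procedure, must be recorded on the Adverse Event eCRF" (protocol 5.3.5.6), the AE tables exist to describe what the study procedures did to patients.

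Exposure to LP begins with the first attempt. A patient enters the SAP safety population through an attempted LP alone (SAP 4.1.1). If the reference then moves to the repeat, an event caused by the failed attempt falls on a negative study day and meets no condition for the tables, although protocol 4.5.6 requires an AE review on the day of the repeat.

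For these events the rule can only lower the tabulated count. What is at stake is the completeness of the system organ class, preferred term and severity tables, not any efficacy or biomarker result.

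**Working it through.** The plan gives no figure to reproduce. The check applies the SAP's own date rules and then sizes the loss under stated assumptions.

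**Step 1: study days.** SAP Section 4 sets Study Day = onset − reference + 1 when onset is on or after the reference, and onset − reference when it is earlier. Count days from the failed LP (day 0). The repeat gaps are illustrative values within the 14-day limit.

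| Repeat (day) | AE onset (day) | Study Day, reference at last LP | After the reference date? | Study Day, reference at first LP |
|---|---|---|---|---|
| 1 | 0 | 0 − 1 = −1 | no | 1 |
| 7 | 1 | 1 − 7 = −6 | no | 2 |
| 7 | 10 | 10 − 7 + 1 = 4 | yes | 11 |
| 14 | 1 | 1 − 14 = −13 | no | 2 |
| 14 | 13 | 13 − 14 = −1 | no | 14 |
| 14 | 14 | 14 − 14 + 1 = 1 | no, if dates are compared | 15 |
| 14 | 15 | 15 − 14 + 1 = 2 | yes | 16 |

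Every onset between the attempts fails the condition. An onset on the date of the reference LP depends on whether the comparison uses the date (Section 4 defines a date) or the clock time (4.7.2 speaks of a time point). That ambiguity reaches every patient's baseline LP.

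**Step 2: who is not affected by the between-attempt gap.** If a failed baseline LP is not repeated, it is itself the last LP, so its later AEs count. Failed LPs at Months 3, 9 and 15 come after the reference.

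**Step 3: size.** The documents give neither a repeat rate nor an AE risk. Assume:

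- f = share of baseline LPs repeated on a later day, 0.02 to 0.15.
- p = AE risk per attempt, 0.10 to 0.30, the same for failed and successful attempts.
- q = share of the failed attempt's AEs that start before the repeat. q = 1 is the upper bound.

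*Patients with an omitted AE, per 100* = 100·f·p·q.
- q = 1: 100 × 0.02 × 0.10 = 0.2, up to 100 × 0.15 × 0.30 = 4.5.
- q = 0.5: 0.1 to 2.25.

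*Fall in patients with any tabulated AE, per 100* = 100·f·p·q·(1 − p)^4. A patient drops out of this count only if the four other LPs (repeat, Months 3, 9 and 15), taken as independent, produce no AE.
- q = 1, lowest: 100 × 0.02 × 0.10 × 0.9^4 = 0.13.
- q = 1, highest: 100 × 0.15 × 0.20 × 0.8^4 = 1.23, because p(1 − p)^4 peaks at p = 0.20.
- q = 0.5: 0.07 to 0.61.

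*Share of LP-related AEs omitted* = q·f/(4 + f): four scheduled LPs plus f repeats per patient, with p cancelling.
- q = 1: 0.02/4.02 = 0.50% to 0.15/4.15 = 3.61%.
- q = 0.5: 0.25% to 1.81%.

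**The case against.** **The repeat may not belong to visit Day 1.** Protocol 4.5.6 calls it an additional visit, and SAP 4.7 shows only scheduled visits in summary tables. If the repeat is not mapped to visit Day 1, the reference stays at the first attempt and the multi-day gap disappears. The distinction between first and last LP in SAP 4.4 could also refer to attempts on the same or adjacent days. This stands as a premise that the documents do not settle. However, the word 'last' in Section 4 has little purpose unless later repeats can count.

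**The exclusion is inferred.** SAP 4.7.2 does not say that only later AEs are summarized, and it also carries a tabulation sentence with no onset limit. This is true, and it lowers confidence. But if every AE were summarized anyway, the onset condition would do nothing.

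**The SAP may be narrower than the protocol.** SAP Section 1 says that its language supersedes the protocol's where specified. A reader might infer that departing from protocol 6.5 is an error in itself; that provision means it is not. The inconsistency that counts lies inside the SAP: with the from-consent sentence in 4.7.2, and with the first-LP anchor in 4.4 and 4.7.7.

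**The stakes are low.** The study is exploratory, all AEs are listed, and serious AEs, deaths and AEs leading to discontinuation are also analysed separately. This stands and sets the priority, although 4.7.2 does not say whether the onset condition applies to those separate analyses.

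**Conclusion.** The point holds as a drafting gap of minor priority, with moderate confidence. It rests on two inferences: that the onset condition limits the tables, and that a later repeat is mapped to visit Day 1. Both are the more natural reading, and neither is stated outright.

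A reader might infer that AEs of failed punctures in general are lost. The documents do not support that, because only baseline failures repeated on a later day fall into the gap. Nor do they support a claim of materially distorted safety results. The assumed rates give at most 0.2–4.5 patients per 100 with an omitted AE and a fall of at most about 0.1–1.2 per 100 in the any-AE count. Both halve if only half of the onsets precede the repeat. The inputs are assumptions, so these ranges illustrate the scale and do not estimate it. No figure is offered for same-day onsets, because that loss depends on how the reference is read.

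**What to change.** In SAP 4.7.2, replace the onset condition with one of two wordings, for the safety population:

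- **Minimum:** summarize AEs with onset on or after the first baseline LP, attempted or successful. This closes the between-attempt gap and matches the anchor used for the vital-signs baseline and the C-SSRS.
- **Broader:** summarize AEs with onset on or after informed consent. This matches the onset rule in the preceding sentence of 4.7.2 and the absence of a cut-off in protocol 6.5. The match is on onset only, since the safety population in protocol 6.5 is wider than the SAP's. This wording also brings in AEs of screening procedures, which goes beyond the gap and is a matter of choice.

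Writing 'on or after' also settles AEs that start on the day of the anchor: under the minimum wording the day of the first LP, and under either wording the day of a later repeat. State that the same onset rule applies to the summaries of serious AEs, AEs leading to discontinuation, and deaths. The last-LP date can stay for study-day calculation.

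The cost is a one-sentence SAP change plus the clarification on the separate summaries. No new data, visit or procedure is needed.
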